9.1.2 Definition of Serious Adverse Events (SAE)

An adverse event (AE) or suspected adverse reaction is considered "serious" if, in the view of either the investigator or sponsor, it results in any of the following outcomes:

- death.
- a life-threatening adverse event,
- inpatient hospitalization or prolongation of existing hospitalization,
- a persistent or significant incapacity or substantial disruption of the ability to conduct normal life functions, or
- a congenital anomaly/birth defect.

Important medical events that may not result in death, be life-threatening, or require hospitalization may be considered serious when, based upon appropriate medical judgment, they may jeopardize the participant and may require medical or surgical intervention to prevent one of the outcomes listed in this definition. Examples of such medical events include allergic bronchospasm requiring intensive treatment in an emergency room or at home, blood dyscrasias or convulsions that do not result in inpatient hospitalization, or the development of drug dependency or drug abuse. A planned medical or surgical procedure is not, in itself, an SAE.

9.1.3 Classification of an Adverse Event

9.1.3.1 Severity of Event

For adverse events (AEs) not included in CTCAE version 5.0, the following guidelines will be used to describe severity.

- **Mild** Events require minimal or no treatment and do not interfere with the participant's daily activities.
- **Moderate** Events result in a low level of inconvenience or concern with the therapeutic measures. Moderate events may cause some interference with functioning.

• **Severe** – Events interrupt a participant's usual daily activity and may require systemic drug therapy or other treatment. Severe events are usually potentially life-threatening or incapacitating. Of note, the term "severe" does not necessarily equate to "serious".

Version Date: 11/16/2021

9.1.3.2 Relationship to Study Intervention

All adverse events (AEs) must have their relationship to study intervention assessed by the clinician who examines and evaluates the participant based on temporal relationship and his/her clinical judgment. The degree of certainty about causality will be graded using the categories below. Relationship of the adverse event to brachytherapy and packing system will be assessed separately. In a clinical trial, the study product must always be suspect.

- Definitely Related There is clear evidence to suggest a causal relationship, and
 other possible contributing factors can be ruled out. The clinical event, including
 an abnormal laboratory test result, occurs in a plausible time relationship to study
 intervention administration and cannot be explained by concurrent disease or other
 drugs or chemicals. The response to withdrawal of the study intervention
 (dechallenge) should be clinically plausible. The event must be pharmacologically
 or phenomenologically definitive, with use of a satisfactory rechallenge procedure
 if necessary.
- Probably Related There is evidence to suggest a causal relationship, and the
 influence of other factors is unlikely. The clinical event, including an abnormal
 laboratory test result, occurs within a reasonable time after administration of the
 study intervention, is unlikely to be attributed to concurrent disease or other drugs
 or chemicals, and follows a clinically reasonable response on withdrawal
 (dechallenge). Rechallenge information is not required to fulfill this definition.
- Possibly Related There is some evidence to suggest a causal relationship (e.g., the event occurred within a reasonable time after administration of the trial medication). However, other factors may have contributed to the event (e.g., the participant's clinical condition, other concomitant events). Although an AE may rate only as "possibly related" soon after discovery, it can be flagged as requiring more information and later be upgraded to "probably related" or "definitely related", as appropriate.
- Unlikely to be related A clinical event, including an abnormal laboratory test result, whose temporal relationship to study intervention administration makes a causal relationship improbable (e.g., the event did not occur within a reasonable time after administration of the study intervention) and in which other drugs or chemicals or underlying disease provides plausible explanations (e.g., the participant's clinical condition, other concomitant treatments).
- **Not Related** The AE is completely independent of study intervention administration, and/or evidence exists that the event is definitely related to another

etiology. There must be an alternative, definitive etiology documented by the clinician.

Version Date: 11/16/2021

9.1.3.3 Expectedness

The treating investigator will be responsible for determining whether an adverse event (AE) is expected or unexpected. An AE will be considered unexpected if the nature, severity, or frequency of the event is not consistent with the risk information previously described for the study intervention and/or this population. Expected AEs are described in *Table 2*.

Table 2

| Adverse event | Maximum grade expected |
|----------------------|------------------------|
| Diarrhea | 3 |
| Cystitis | 2 |
| Rectal perforation | 3 |
| Rectal fistula | 3 |
| Proctitis | 3 |
| Rectal pain | 2 |
| Rectal hemorrhage | 3 |
| Bowel perforation | 3 |
| Bladder perforation | 2 |
| Hematuria | 2 |
| Urinary frequency | 2 |
| Urinary incontinence | 2 |
| Urinary urgency | 2 |
| Pelvic pain | 2 |
| Vaginal perforation | 3 |
| Vaginal hemorrhage | 2 |

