2.2.5 Relevant Clinical Experience

The investigational product has been used in cadavers, but not in living humans. Data related to cadaver studies, biocompatibility and leakage studies may be found in the investigator's brochure.

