9.1.6 Adverse Event Reporting

AEs must be recorded into the EDC system designated by the University of Virginia database, per the following guidelines.

Table 3

| | Reporting req | uirements f | or AEs that oc | Table 3: High R ccur within 30 da | | se of protocol s | pecified treatme | nt |
|----------------------------------|-------------------|-------------|----------------|--------------------------------------|----------------------|-------------------------|----------------------|---------------------|
| | Grade 1 | Grade 2 | | Grade 3 | | | | Grade 4 & 5 |
| | Expected | | | Expected | | Unexpected | | Expected |
| | and Unexpected | Expected | Unexpected | Without hospitalization | With hospitalization | Without hospitalization | With hospitalization | and Unexpected |
| Unrelated Unlikely | 30 days | 30 days | 30 days | 30 days | 15 days | 30 days | 15 days | 7 days |
| Possible Probable Definite | 30 days | 30 days | 15 days | 30 days | 15 days | 7 days | 7 days | (24-hrs)* 7 days |

^{*}Enter into Cancer Center database within 24 hours if unexpected and definitely related to protocol specified treatment Hospitalization defined as an inpatient hospital stay or prolongation of a hospital stay equal to or greater than 24 hours

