9.1.7 Serious Adverse Event Reporting

The study clinician will report to the overall study PI any serious adverse event, whether or not considered study intervention related, including those listed in the protocol or clinical use instructions, and must include an assessment of whether there is a reasonable possibility that the study intervention caused the event. See Study Reference Manual for contact information and instructions for reporting.

All serious adverse events (SAEs) will be followed until satisfactory resolution or until the site investigator deems the event to be chronic or the participant is stable. Other supporting documentation of the event may be requested by the UVA Coordinating Center (UVA CC) and should be provided as soon as possible.

Site Reporting Requirements

Any Event Resulting in death that is deemed DEFINITELY related to (caused by) study participation

OR

Any event deemed serious

 Report to the UVA CC within 24 hours from the time the study team received knowledge of the event according to UVA CC requirements.

Version Date: 11/16/2021

- Non relying sites: report to your IRB in accordance with your IRB guidelines.
- Relying sites (use the UVA IRB-HSR as the IRB of record): the UVA CC will report to the UVA IRB-HSR in accordance with the guidelines.
- UVA site: report to the UVA IRB-HSR in accordance with the guidelines.

UVA Reporting Guidelines

- Notify the UVA IRB-HSR of any event resulting in death that is deemed DEFINITELY related to (caused by) study within 24 hours from the time the study team received knowledge of the event. Report using IRB Online and by telephone.
- Notify the UVA IRB-HSR of any serious, unexpected and related adverse event within 7 calendar days from the time the study team receives knowledge of the event. Timeline includes submission of signed hardcopy of AE form. Report using IRB online.
- For events considered at least possibly related to BrachyGel, notify Brachyfoam within 72 hours of UVA CC's awareness of the event. To do so, email [contact].

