9.2 Unanticipated Adverse Device Effects

9.2.1 Definition of Unanticipated Adverse Device Effect (UADE)

Unanticipated adverse device effect is any serious adverse effect on health or safety or any life-threatening problem or death caused by, or associated with a device, if that effect, problem, or death was not previously identified in nature, severity, or degree of incidence in the investigational plan or application (including a supplementary plan or application), or any other unanticipated serious problem associated with a device that relates to the rights, safety, or welfare of subjects (21 CFR 812.3(s)).

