10.5 Safety Monitoring

All study participants who receive treatment will be assessed for the occurrence of treatment related adverse events. Adverse events of potential concern related to the vaginal packing, are acute vaginal adverse events (aVAE) which: i) is determined to be at least possibly related to BrachyGel; ii) occurs within the first 30 days from 1st Brachytherapy treatment utilizing BrachyGel (ie. Period 2 or 3 depending on the randomization arm); and iii) meets the criterion below:

Has any of the following vaginal toxicities grade >= 3 according to CTCAE:

- Vaginal pain
- Vaginal perforation
- Vaginal hemorrhage
- Vaginal inflammation
- Vaginal infection
- Dyspareunia

Safety will be assessed by monitoring the number of participants who experience an aVAE. Results reported in Romano et al 2017 on high-dose brachytherapy experience at UVA noted that 0/74 = 0% (upper limit of 95% CI of 4.9%) patients experienced grade ≥3 aVAE.²⁰ Others have reported similarly low rates with at most 2% for late vaginal toxicity.^{21,22} For this study the upper boundary of a sequential probability ratio test (SPRT) based upon a binomial test of proportions for aVAE will be used for monitoring, to protect against excessive aVAE rates. The stopping boundary is for a SPRT contrasting a null 4% versus an unacceptable 9% aVAE rate, with nominal type I and II errors of 10% and 10%, respectively. The slope of the parallel line for monitoring is 2.54 and the intercept is 0.062.

Safety stopping guidelines for the occurrence of aVAEs are detailed in the following table. If a stopping bound is crossed then accrual to the study will be suspended until the study PI, co-investigators and the DSMC can review the data, and determine if the study should continue, be amended or be closed to further accrual.

| Number of participants who received BrachyGel | Number with grade ≥ 3 aVAE | | |
|---|----------------------------|--|--|
| 3-7 | ≥ 3 | | |
| 8-23 | ≥ 4 | | |
| 24-39 | ≥ 5 | | |
| 40-45 | ≥ 6 | | |

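### A single expectedness list covers both brachytherapy and the device, so a BrachyGel-related Grade 3 perforation can be classed as expected, losing the 7-day IRB report and possibly UADE status

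*Combined protocol and SAP*

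**What the plan says.** Section 9.1.3.2 asks for two causality judgements on each adverse event, one for brachytherapy and one for the packing system. Section 9.1.3.3 then defines expectedness against risk information for the intervention and/or the population, and gives one list, Table 2, with a maximum expected grade per event. Three entries matter here: "Vaginal perforation | 3", "Rectal perforation | 3" and "Bowel perforation | 3".

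On the device, section 2.2.5 states: "The investigational product has been used in cadavers, but not in living humans". Section 2.3.1 lists urinary, rectal, bowel and vaginal morbidity after brachytherapy, including fistula, bleeding and stenosis, but no perforation. The only packing-specific risk it names is short-lived local pain.

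Expectedness is then used in three places:
- Section 9.1.7: "Notify the UVA IRB-HSR of any serious, unexpected and related adverse event within 7 calendar days".
- Section 9.2.1: a UADE is a serious effect that "was not previously identified in nature, severity, or degree of incidence in the investigational plan" or application.
- Table 3 in section 9.1.6: the row for related events begins "Possible Probable Definite | 30 days | 30 days | 15 days | 30 days". The fourth period is for an expected Grade 3 event without hospitalization. The row continues with 15 days for an expected Grade 3 event with hospitalization, and 7 days for an unexpected one in either case.

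**The concern.** Table 2 reads as a background list for pelvic brachytherapy. Because it is not divided by cause, it also governs events that the clinician attributes to the packing. BrachyGel works by expanding in place and displacing tissue (section 2.2.3), so mechanical injury is a hazard that a first-in-human study would want to isolate. A perforation attributed to the device is what the IRB report and the UADE evaluation are there to catch. Yet the plan names it in advance as expected at Grade 3, and the protocol gives no human device experience to support that. At stake is whether the IRB and the UADE process see such an event promptly and as a new device signal.

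**Working it through.** **1. Basis for calling a device perforation expected.** Section 2.2.5 reports cadaver use only, and section 2.3.1 gives no perforation rate. Section 10.5 cites a UVA series in which "0/74 = 0% (upper limit of 95% CI of 4.9%) patients experienced grade ≥3 aVAE". The upper limit reproduces: 1 − 0.025^(1/74) = 0.0486, or 4.9%. That series concerns vaginal events under brachytherapy. It does not bear on rectal or bowel perforation, and it does not exclude vaginal rates below 4.9%. The argument therefore rests on the lack of device experience, not on 0/74.

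**2. What the expected label changes.** Take a Grade 3 perforation judged at least possibly related to BrachyGel.

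| Route | Depends on expectedness? | Effect of the label |
|---|---|---|
| IRB report, 7 days (9.1.7) | Yes | Lost, even if serious |
| UADE status, with evaluation in 10 working days (9.2) | Yes, through prior identification in the plan | May be lost |
| Table 3 entry, no hospitalization | Yes | 30 days instead of 7 |
| Table 3 entry, hospitalization | Yes | 15 days instead of 7 |
| Serious event to coordinating center, 24 hours (9.1.7) | No | None |
| Any SAE to the overall study PI (9.1.7) | No; includes protocol-listed events | None |
| Manufacturer notice, 72 hours from the coordinating center's awareness (9.1.7) | No; relatedness only | None directly |
| aVAE stopping rule (10.5) | No | None on whether the event counts |

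**3. Overlap with the stopping rule.** Section 10.5 counts six vaginal toxicities at Grade 3 or above. Only vaginal perforation is also expected at Grade 3 in Table 2. Vaginal hemorrhage is capped at Grade 2 there, and the other four are not listed. Rectal and bowel perforation are not among the six, so they never enter the count.

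**4. Largest delay the label can add.** Inputs are 57 participants (section 10.4) over 14 months (synopsis), with even accrual and 30.44 days per month assumed.
- Accrual rate: 57 / 14 = 4.07 per month; 4.07 / 30.44 = 0.134 per day.
- No hospitalization: 30 − 7 = 23 days; 23 × 0.134 = 3.1 participants.
- Hospitalization: 15 − 7 = 8 days; 8 × 0.134 = 1.1 participants.

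Inpatient hospitalization makes an event serious under section 9.1.2, so it reaches the coordinating center within 24 hours anyway. The 8 days are then a matter of database entry. The 23 days can affect the stopping count only for a vaginal perforation that is not reported as serious, and only if the count is taken from Table 3 entries. Section 10.5 does not say how the count is fed.

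**The case against.** The strongest reply is that the safety net is mostly intact. Any serious event goes to the coordinating center within 24 hours whatever its expectedness. Section 9.1.2 lets an investigator call an event serious without hospitalization if it may jeopardize the participant and need intervention. The manufacturer hears of related events, and the DSMC reviews all adverse events monthly. This stands. A reader might infer from Table 2 that device-related perforations escape expedited reporting altogether; the documents do not support that.

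A reader might also infer that these perforations reach the stopping rule late, perhaps late enough to pass through a whole row of the stopping table. That does not hold either. The rule ignores expectedness, and rectal and bowel events are outside it. The monthly DSMC interval applies equally to unexpected events, so it cannot be charged to the label. The narrowest row (3 to 7) covers five exposed participants, against at most about 3 accrued in the extra 23 days.

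Third, expectedness also turns on frequency, and the UADE definition on degree of incidence, so an investigator could still call a perforation unexpected. This stands in part. With no perforation rate given, there is no benchmark, and two sites could classify the same event differently.

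Finally, the investigator's brochure and the device labeling were not available for this review and may carry device risk information. Section 2.2.5 describes the brochure's relevant data as cadaver, biocompatibility and leakage studies. That leaves no human experience, but it is a reason to point the fix at device-specific risk information.

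**Conclusion.** The point holds in a limited form. Relatedness is split by cause and expectedness is not. Following Table 2 as written, a serious Grade 3 vaginal, rectal or bowel perforation related to BrachyGel can be classed as expected. It then loses the 7-day IRB report, may lose UADE status with its evaluation duties, and has 30 days (15 with hospitalization) for database entry instead of 7. The first two consequences matter most, and they do not depend on any accrual assumption.

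The effect on the stopping count is small and conditional: at most 23 days, or about 3 participants at even accrual, for vaginal perforation that is not reported as serious, and only if counting follows Table 3. The stopping boundaries, sample size and primary analysis are unaffected. The change is worth making because it is cheap and closes a reporting gap for a device new to living humans.

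**What to change.** In section 9.1.3.3, state that Table 2 governs expectedness only for events attributed to brachytherapy. Events at least possibly related to BrachyGel should be judged separately against the device's own risk information, so that device-related Grade 3 perforations are treated as unexpected for Table 3, the section 9.1.7 IRB report and the UADE assessment.

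In section 9.1.6, add that any event meeting the section 10.5 aVAE criteria is reported to the coordinating center on the existing 24-hour route, whether or not it is serious or expected. The stopping count then stays current, and the 72-hour manufacturer notice, which runs from the coordinating center's awareness, starts promptly for these events too.

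The cost is a few sentences of text and a few additional expedited reports. No treatment, boundary or sample size changes.

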9.1.4 Abnormal Laboratory Values

Laboratory values will not be collected or assessed for this study. Abnormal laboratory values will not be recorded or reported in this study.

9.1.5 Time Period and Frequency for Event Assessment and Follow-Up

The occurrence of an adverse event (AE) or serious adverse event (SAE) may come to the attention of study personnel during study visits and interviews of a study participant presenting for medical care, or upon review by a study monitor.

All AEs including local and systemic reactions not meeting the criteria for SAEs will be captured on the appropriate case report form (CRF). Information to be collected includes event description, time of onset, clinician's assessment of severity, relationship to study product (assessed only by those with the training and authority to make a diagnosis), and time of resolution/stabilization of the event. All AEs occurring while on study must be documented appropriately regardless of relationship. All AEs will be followed to adequate resolution.

Any medical condition that is present at the time that the participant is screened will be considered as baseline and not reported as an AE. However, if the study participant's condition deteriorates at any time during the study, it will be recorded as an AE.

Changes in the severity of an AE will be documented to allow an assessment of the duration of the event at each level of severity to be performed. AEs characterized as intermittent require documentation of onset and duration of each episode.

Version Date: 11/16/2021

Study staff will record all reportable events with start dates occurring any time after brachytherapy fraction 2 is completed until 30 days (for non-serious AEs) or anytime (for SAEs considered related to the study intervention) after the last day of study treatment. At each study visit, the investigator will inquire about the occurrence of AE/SAEs since the last visit. Events will be followed for outcome information until resolution or stabilization.

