3 OBJECTIVES AND ENDPOINTS

| Objectives | Endpoints |
|--|---|
| Primary | |
| To determine if BrachyGel Vaginal Hydrogel Packing System (BrachyGel) is non-inferior to standard method vaginal packing (standard) in dose thresholds for the rectum and the bladder. | The dose to the hottest 2 cc (D2cc) (in Gy) for the rectum and the bladder in periods 1 and 2 (e.g. fractions 2 and 3). |
| Secondary | |
| To estimate the difference in the safety profile of BrachyGel compared to standard vaginal packing. | Frequency, intensity, and duration of adverse events in periods 1 to 4 (e.g. fractions 2 through 5). |
| To estimate period effects in dosimetry thresholds (D0.1cc, D1cc, D2cc) between BrachyGel and standard vaginal packing for the rectum and the bladder. | The dose to the hottest 0.1 cc (D0.1cc), 1 cc (D1cc), and 2 cc (D2cc) (in Gy) for the rectum and the bladder in periods 1 through 4 (e.g. fractions 2 through 5). |
| Exploratory | |
| To estimate the difference in participant- reported discomfort between BrachyGel and standard vaginal packing. | Participant-reported discomfort from packing scored on a 4-point scale for periods 1 through 4 (e.g. fractions 2 through 5). |

| To estimate the difference in physician/physicist evaluation of imaging properties and completeness of packing between BrachyGel and standard vaginal packing. | Physician/physicist evaluation of imaging properties and completeness of packing scored on a 4-point scale for periods 1 through 4 (e.g. fractions 2 through 5). |
|--|--|
| To estimate the difference in physician-scored use experience between BrachyGel and standard vaginal packing. | Physician-scored use experience scored on a 4-point scale for periods 1 through 4 (e.g. fractions 2 through 5). |

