6 STUDY INTERVENTION

6.1 Description of Study Intervention(s)

Participants will be assigned to Arm A or Arm B, as described in section 4.1 and Figure 1. Fraction 1 for all participants (both Arms) will receiving standard of care packing. During fractions 2-5 of brachytherapy, participants will have vaginal packing alternating between the BrachyGel Vaginal Hydrogel Packing System and standard of care vaginal packing, strategy which will include gauze vaginal packing or rectal retractor.

For Arm A of the study, the BrachyGel Packing System will be used during fractions 3 and 5. Standard packing will be used for fractions 1, 2 and 4.

For Arm B of the study, the BrachyGel Packing System will be used during fractions 2 and 4. Standard packing will be used for fractions 1, 3 and 5.

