10.3 Evaluation of Sample Populations and Criteria

10.3.1 Study Population

Safety: All randomized participants receiving at any protocol treatment will be evaluated for safety outcomes.

Evaluable: All randomized eligible participants receiving at least 3 fractions of treatment will be evaluated for study outcomes.

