10.3.2 Study Outcomes & Endpoints

Study measurements will be captured post each fraction of treatment. Assessments may include:

- Adverse events
- Dosimetry
- Physicist evaluation of imaging/packing
- Physician evaluation of imaging/packing
- Participant discomfort survey

There are two primary endpoints based upon dosimetry measurements in the bladder and the rectum. Each endpoint is the difference between D2cc dosimetry measurements obtained during periods 1 and 2 (fractions 2 and 3 under the 2x2 crossover structure). Additional assessments include data from periods 3 and 4 (fractions 4 and 5).

Additional endpoints include measurements over all periods for:

- Bladder and rectal dosimetry as measured by D0.1 cc and D1 cc.
- Participant reported discomfort
- Physicist evaluated imaging properties
- Physician evaluated imaging properties
- Physician evaluated use experience

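### Section 9.1.5 starts adverse event recording only after fraction 2 ends, but the safety endpoint and the vaginal-toxicity stopping rule both need fraction 2, which is Arm B's first BrachyGel use

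*Combined protocol and SAP*

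**What the plan says.** The recording window is set in 9.1.5: "Study staff will record all reportable events with start dates occurring any time after brachytherapy fraction 2 is completed". It closes 30 days after the last study treatment for non-serious events and stays open for related serious ones.

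Other sections place fraction 2 inside the safety data:

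- Section 6.1: "For Arm B of the study, the BrachyGel Packing System will be used during fractions 2 and 4". Arm A first receives BrachyGel at fraction 3. Section 4.1 numbers fractions 2 to 5 as periods 1 to 4.
- Section 3, secondary safety endpoint: "Frequency, intensity, and duration of adverse events in periods 1 to 4 (e.g. fractions 2 through 5"). Section 10.6 summarises adverse events over the same fractions by packing type.
- Section 10.5: "All study participants who receive treatment will be assessed for the occurrence of treatment related adverse events". An aVAE counts towards the stopping rule if it is at least possibly related to BrachyGel, is one of the listed vaginal toxicities at grade 3 or higher, and falls within 30 days of the first BrachyGel fraction.
- Schedule of Activities (13.1): footnote 4 makes Brachytherapy 2 the start of treatment, and the adverse event review row is marked at that visit.
- Section 9.1.5 itself: "All AEs occurring while on study must be documented appropriately regardless of relationship".

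**The concern.** The sentence that tells staff what to record excludes the procedure at which half of the participants first meet the device. Section 2.2.5 says the product has been used in cadavers but not in living people. Several of the listed aVAE types (vaginal pain, perforation, hemorrhage) could plausibly begin while packing is being placed or is in position, and 2.3.1 itself expects localized pain from packing during the procedure.

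If sites apply the sentence as written, absolute event rates for fractions 2 to 5 would be undercounted. Any aVAE that goes missing can only delay or prevent the suspension of accrual that 10.5 provides for.

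**Working it through.** **1. Is fraction 2 inside the intended safety period?** Yes. Registration must precede fraction 2 (6.4), fraction 2 is the start of treatment (13.1), and it is period 1 (4.1). The endpoint in section 3, the summary in 10.6 and the aVAE window in 10.5 all include it. The 9.1.5 start sentence does not.

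**2. What falls in the gap?** Events that begin during placement or dwell at fraction 2. Later events on the same day are inside the window if they start after completion. The boundary is loose: the sentence refers to dates, while 9.1.5 also collects time of onset. Completion is not defined, and schedule footnote 3 puts packing removal after completion of brachytherapy, so the status of removal is unclear.

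**3. Does serious event reporting close the gap?** Only in part. Section 9.1.7 covers all serious events with no fraction 2 limit. The aVAE criterion, however, is grade, not seriousness. Section 9.1.3.1 notes that severe does not necessarily mean serious, and Table 3 has columns for grade 3 events without hospitalization.

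**4. Exposure.** With the planned 20 evaluable participants per arm (10.4):

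- BrachyGel placements: 40 × 2 = 80, of which 20 (25%) are Arm B's fraction 2.
- First BrachyGel exposures: 40, of which 20 (50%) are Arm B's fraction 2.
- Standard placements in fractions 2 to 5: 80, of which 20 (25%) are Arm A's fraction 2.

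These count placements, not lost events.

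**5. The plan's own boundary.** With p0 = 0.04, p1 = 0.09 and both errors 10%, the odds ratio is 0.09 × 0.96 / (0.04 × 0.91) = 2.374, with log 0.8644. The intercept is ln(0.9/0.1)/0.8644 = 2.54 and the slope is ln(0.96/0.91)/0.8644 = 0.062. Rounding 2.54 + 0.062n up gives every row of the printed table for n = 3 to 45. (The sentence in 10.5 swaps the two names; the table is right.)

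**6. Illustration only.** The documents give no share of aVAEs that begin during a procedure. Assume a share s, split evenly over Arm B's two BrachyGel placements. These are two gaps of 2 to 7 days apart (1.1), that is 4 to 14 days, so both lie inside the 30-day window. At most f = s/2 of Arm B's aVAEs would then be lost. The figures below take a true 9% rate, the printed boundary checked after each participant, arms alternating 1:1 and at most one aVAE per participant. Expected recorded aVAEs among 45 are 45 × 0.09 × (1 − f/2). Ranges reflect which arm enrols first.

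| s | f (at most) | Crossing by 40 | Crossing by 45 | Expected recorded among 45 |
|---|---|---|---|---|
| 0 | 0 | 29.5% | 31.5% | 4.05 |
| 10% | 5% | 27.8–27.9% | 29.6–29.7% | 3.95 |
| 20% | 10% | 26.0–26.2% | 27.7–27.9% | 3.85 |
| 50% | 25% | 20.9–21.4% | 22.3–22.8% | 3.54 |

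The losses are upper limits for each s, because serious aVAEs are still reported. The low 31.5% with full capture is a property of the boundary, not of the 9.1.5 sentence.

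**7. The label in 10.5.** Its parenthesis places first BrachyGel use in period 2 or 3. By 4.1 and 6.1 it is period 1 (Arm B) or period 2 (Arm A). The printed numbers fit only if read as fractions.

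**The case against.** The best reply is that a sensible site would not lose these events. The schedule marks adverse event review at Brachytherapy 2, and 8.1.2 has a clinician evaluate each participant at every study visit. Loss occurs only if one sentence overrides those instructions. This stands, and it makes the problem a contradiction that can lose events rather than a certain loss. It does not remove the contradiction, because the overriding sentence is the one that defines what staff record.

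The residue is also narrow: non-serious grade 3 or higher aVAEs starting during one placement, plus milder events that matter only for the summaries. Under the two smaller assumed shares, the crossing probability moves by only about two to four percentage points. That stands too.

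Some passages that seem to add further contradictions are weak support:

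- Section 10.3.1, under which treated participants "will be evaluated for safety outcomes", defines a population, not a recording window.
- Section 10.3.2, "Study measurements will be captured post each fraction of treatment", is compatible with recording after completion, and lists adverse events only among assessments that may be included.
- The deterioration rule in 9.1.5, "condition deteriorates at any time during the study, it will be recorded as an AE", concerns conditions already present at screening.
- The on-study rule in 9.1.5 conflicts less directly, since documenting and recording reportable events could be read as separate duties.

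The endpoint and aVAE conflicts do not depend on any of these.

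**Conclusion.** The contradiction is real and should be fixed. Taken literally, the 9.1.5 start sentence leaves out non-serious events, including non-serious grade 3 or higher aVAEs, that begin during placement or dwell at Arm B's first BrachyGel exposure. Confidence is high for the contradiction and not for any particular effect on the monitor: the table above rests on assumed shares.

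Three stronger readings are tempting, and the documents do not support them:

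- **That fraction 2 events will be lost.** The schedule and 8.1.2 point the other way, and serious events have their own route.
- **That the stopping rule is disabled.** Losing every Arm B aVAE would cut crossing by 45 participants to 3–4%. That would require all of them to begin during fraction 2 and none to be serious, which nothing in the plan suggests.
- **That the comparison favours BrachyGel.** Arm A's standard placement at fraction 2 falls in the same gap, so there is no clear bias between packing types. The primary dosimetry endpoint is unaffected. The one-sidedness applies only to the aVAE count, to which Arm A's standard placement at fraction 2 does not contribute.

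**What to change.** - **9.1.5:** record events with onset from the start of the fraction 2 procedure, before packing insertion, through packing removal and onward.
- **9.1.5, on-study sentence:** state how events between registration and fraction 2 are handled. Section 6.4 allows registration before fraction 1, so a start at fraction 2 does not by itself satisfy that sentence.
- **10.5:** change the label for first BrachyGel use to period 1 or 2 (fraction 2 or 3).
- **Separate clarification:** 9.1.1 limits adverse events to those at least possibly related, while 9.1.5 and Table 3 also take in unrelated ones. Section 9.1.3.2 rates brachytherapy and packing separately, so 9.1.1 should say which relationship it means. This does not affect the stopping rule.

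The cost is a few sentences and matching case report form instructions. The start-point change needs no new visit, because review is already marked at Brachytherapy 2. As printed, the schedule row marks review only at Brachytherapy 2, Brachytherapy 5 and follow-up, while 8.1.2 requires evaluation at every visit; the two should be aligned in the same amendment.
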